12.2 Analysis of Outcome Measures

- Best overall response will be reported as the number and proportion of patients in each response category, and overall, during the first 6 cycles of treatment. In addition, best response observed after 6 cycles until the end of the trial will be reported by category and overall.
- The number and proportion of patients experiencing toxicity, including haematological and nonhaematological toxicity, will be reported with 95% confidence intervals.
- Time to event outcomes will be assessed using the method of Kaplan and Meier with point estimates presented at 6, 12, 24 and 36 months with 95% confidence intervals along with median survival time and confidence intervals. A Kaplan meier plot will be produced.
- The mean maximum % decrease during the first 6 cycles of treatment and overall will be reported with 95% confidence intervals

The biomarker study and PET scan analysis at present are exploratory.

There is little data on the expression of mTOR pathway proteins in DLBCL so the aim is to define expression in biopsy samples taken at relapse (or within 3 months). In collaboration with AstraZeneca, we will assess the expression of these proteins (p-S6, p-AKT, and p-4E-BP1) by immunohistochemistry (IHC). These will be measured at relapse, at subsequent progression, and in any tissue obtained at further optimal biopsy at 15 days. This will be initially assessed in 8 patients, with the potential to expand the analysis dependent on response data. We will then seek to determine a cut off which best predicts response to AZD2014, if indeed there is any correlation. Appropriate

statistical models (e.g. area under the curve, logistic regression) will be used to determine the cut off as detailed in the Statistical Analysis Plan.

Other ethically approved research may be performed on these samples if agreed by the trial management group.

All PET and CT scans will be centrally reviewed at St Thomas' using the 5-point scale for visual interpretation (Deauville Criteria and the Lugano classification). Semi-quantitative analysis will also be performed using the published value for Δ SUVmax \geq 66% at 2 cycles to separate good from poor responders but receiver operating characteristic (ROC) curves will also be derived to determine if possible whether the optimal cut-off for patients treated with AZD2014 is similar to the cut-off for patients with DLBCL treated with (R)CHOP chemotherapy (35,38,39). Maximal standardized uptake value reduction is calculated as follows:

SUVmax reduction (%) = 100 x [SUVmax (PET0) - SUVmax (iPET)/SUVmax (PET screening)].

Standard contrast enhanced CT responses will classified according to the International Workshop Criteria (1).

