3. TRIAL DESIGN

This is a prospective, single arm, multicentre, phase II clinical trial utilising a two stage design. Stage one will assess the safety and activity of AZD2014 as a single agent in the treatment of DLBCL in 30 patients. Stage two will assess the additional toxicity of combining AZD2014 with Rituximab in an additional 6 patients.

Stage two will be recruited following the full recruitment of stage 1. Stage 2 recruitment will be staggered with 3 patients recruited and their safety data evaluated prior to the recruitment of the remaining 3 patients.

Post treatment biopsies will be requested at relapse in patients receiving rituximab to assess for evidence of synergy.

It is anticipated that the 36 patients required will be recruited over 18 months from specialist centres including the 13 TAP centres.

Once registered to the study, patients will receive AZD2014 125mg bd on an intermittent schedule of 2 days of treatment followed by 5 days with no treatment. Treatment would be on days 1, 2, 8, 9, 15, 16, 22 and 23 of each course 28 days in duration. Treatment is ongoing until progression or withdrawal due to toxicity or patient's choice. For the second stage of the trial, rituximab 375mg/m² will also be administered intravenously on day 1 of the 28 day cycle for a total of 6 cycles in combination with AZD2014.

All patients will be followed for a minimum of 1 year up until disease progression or death.

For patients still on AZD2014 treatment after 1 year (no progression) treatment should still be reviewed at least 3 monthly. Safety, progression and survival data will be collected every 3 months. Assessments should be as per local practice with a CT scan conducted every 3/4 months.

At progression, patients will then be followed up annually for survival data.

Molecular and free DNA sub-study

Tissue, saliva and blood samples will be collected during treatment to determine the activity of AZD2014 on downstream targets, and correlating with response. This will include biopsy tissue from the pre-treatment sample, any biopsy performed on treatment and at relapse post-AZD2014 should this occur.

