- h) In the monotherapy study ECGs are to be taken on cycle 1 day1 Pre dose and cycle 1 day1, 2hrs post dose. The ECG should be taken on day 1 of subsequent cycles only in instances where the cycle 1 day 1 ECGs were abnormal. In the combination study ECGs should be taken on day 1 cycle 1 pre and post dose and day 1 of each subsequent cycle until indicated otherwise.
- i) CT at the end of every 2 cycles for first 6 cycles, then every 4 cycles (or if clinical suspicion of progression) and at 1 year post treatment start if not progressed on treatment. High resolution CT of the chest should be performed if clinically indicated by pulmonary symptoms any time during the study.
- j) If no longer receiving treatment, every 3-4 months for 1 year from treatment start and / or at clinical suspicion of progression
- k) The cycles 2&6 PET-CT scans should be performed in the 5 day gap between treatments on days 17-21 but ideally as close to the next administration of treatment i.e. days 20/21 to avoid the potential for inflammatory uptake of FDG
- I) Only if disease progression suspected
- m) Treatment will be delivered on a 2 days on 5 days off schedule until disease progression, unacceptable toxicity or patient choice.
- n) Patients with an unresolved adverse reaction (AR) or SAE event at treatment completion or study drug discontinuation will be monitored until the event is resolved, stabilised or the patient is lost to follow up.
- o) (OPTIONAL) Screening, end of cycle 2, end of cycle 6 and/or at progression. Additional samples will be taken in responding patients every 3 months for up to a year
- p) Within 3 months of trial entry and at relapse, mandatory. May include bone marrow if indicated for disease staging.
- q) Optional biopsy on day 15 of cycle 1
- r) To be taken from patients who have consented to the optional sub study which requires the collection of additional blood and saliva samples

Additional optional assessments may be performed at the discretion of the investigator if clinically indicated or in the event of toxicity.

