7.10 Patient Follow Up

Whilst patients remain on trial treatment they will be reviewed on day 1 of every cycle with assessments as per section 7.3. For patients still on AZD2014 treatment after 1 year treatment should be reviewed at least 3 monthly. Assessments should be as per local practice with a CT scan conducted every 3-4 months.

If the patient comes off treatment but has not progressed, they will be reviewed in clinic and with a contrast enhanced CT of the neck, chest, abdomen and pelvis every 3 months for a year from the start of therapy. If the patient has not progressed after 1 year, they will then be followed up in clinic as per local policy with a CT as per local practice or performed on suspicion of progression. Patients will have no specific trial follow up, but their registering physician will be contacted every 6 months to determine progression and survival data.

At progression, patients will then be followed up 6 monthly for survival data.

All patients will be followed up for a minimum of 1 year, after starting treatment or until death.

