12.5 Planned Final Analyses

The first main analysis of the primary outcome measure will be performed after all patients have been treated and followed up for 6 cycles. Subsequent analyses of all outcome measures will be performed after a minimum of 12 months follow up of all patients.

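### Survival contact after progression is annual in section 3 but 6-monthly in section 7.10, and the 36-month estimate is not supported at the earliest planned analysis

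*Protocol*

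**What the plan says.** - **Estimates promised.** Section 12.2 requires, for all time-to-event outcomes, "point estimates presented at 6, 12, 24 and 36 months with 95% confidence intervals".
- **When.** Section 12.5 says that the analyses of all outcome measures, after the first analysis of response, will be "performed after a minimum of 12 months follow up of all patients".
- **Accrual.** Section 3: "It is anticipated that the 36 patients required will be recruited over 18 months". The six combination patients fall at the end of that period: "Stage two will be recruited following the full recruitment of stage 1".
- **Contact after progression.** Section 3: "At progression, patients will then be followed up annually for survival data". Section 7.10: "At progression, patients will then be followed up 6 monthly for survival data".
- **Censoring.** Section 12.1.2 measures OS from registration and censors patients who are alive, lost or off study at their last follow-up date. It also sets a 12-month minimum follow-up, and section 7.10 has the same minimum, counted from the start of treatment.
- **One-year scan.** Progression-free survival (PFS) also runs from registration. Section 7.3, footnote i, times the last fixed on-treatment CT "at 1 year post treatment start if not progressed on treatment", and section 6 allows up to 7 days between registration and treatment.

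**The concern.** A site cannot tell from the protocol whether to report survival once or twice a year after progression. In this disease most patients progress early, so that interval governs most of the survival follow-up.

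The interval matters because of the censoring rule. A death is likely to reach the trials office when it happens, whereas a living patient counts only up to the last contact. Survivors are then removed from the risk set too early and deaths stay in, which pulls the Kaplan-Meier curve down. The longer the interval, the larger the effect.

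The 36-month estimate raises a different question: whether the data it needs will exist when the analysis is done. OS and PFS at 1 year are named secondary outcomes, so it also has to be asked whether either problem reaches back to 12 months.

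**Working it through.** **1. Longest follow-up at the earliest analysis.** Inputs: accrual 18 months (section 3), minimum follow-up 12 months (section 12.5). Maximum = 18 + 12 = 30 months. Assuming uniform accrual, the share of patients with at least L months of potential follow-up is (30 − L)/18, capped at 1.

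| Time point | Share | Of 36 patients |
|---|---|---|
| 6 months | 1 | 36 |
| 12 months | 1 | 36 |
| 24 months | 6/18 = 0.33 | 12 |
| 36 months | 0 | 0 |

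The first patient reaches 36 months only if the cut-off is 36 − 18 = 18 months or more after the last registration, or if accrual takes 36 − 12 = 24 months. All patients reach it 18 + 36 = 54 months after the first registration.

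**2. Expected numbers at risk at 24 months.** Section 1.1 gives two survival figures from cited studies: median OS 7.2 months with a single-agent mTOR inhibitor, and 37% alive at 12 months with everolimus plus rituximab. Under an exponential curve the second implies a median of 12 × ln 2 / (−ln 0.37) = 8.4 months.
- Median 7.2: S(24) = 0.099, so 12 × 0.099 ≈ 1.2 patients at risk.
- Median 8.4: S(24) = 0.37² = 0.137, so 12 × 0.137 ≈ 1.6 patients at risk.

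**3. How the contact interval acts.** Take a patient who progresses at month 3 and is alive at the cut-off with 26 months of follow-up. Annual contact falls at months 15 and 27, so the patient is censored at 15. Six-monthly contact falls at months 9, 15, 21 and 27, so the patient is censored at 21. In truth the patient was alive at 24.

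**4. Size of the effect.** Simulation with 30 patients, uniform accrual over 18 months, cut-off at 30 months and exponential OS. Contacts are counted from progression (median PFS 2.6 months, section 1.1). Deaths are known at once, and living patients are censored at last contact. Over median OS of 7.2 to 8.4 months:

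| Contact | Bias in 24-month OS | Bias in 12-month OS, minimum not enforced | Bias in 12-month OS, 12-month minimum enforced |
|---|---|---|---|
| Annual | about −5 to −6 points | about −2 to −3 points | about 0 |
| 6-monthly | about −3 points | about −1 point | about 0 |

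The true 24-month values are only 9.9% and 13.7%, so 5 to 6 points is close to half of the quantity being estimated.

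**5. One-year PFS.** On-treatment CTs fall on days 56, 112, 168, 280, about 365 and 392 from treatment start. With a lag of 0 to 7 days, the 1-year CT falls on day 365 to 372 from registration. Where the lag is a day or more, progression first seen on that CT is dated just after the 12-month reading.

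**The case against.** Three points can be made for the protocol.

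**The 36-month estimate.** A reader might infer that it can never be produced. The text does not support that. Twelve months is a minimum, section 12.5 speaks of analyses in the plural, the 18 months is only anticipated, section 7.10 continues 6-monthly contact without an end date, and section 11 sets no calendar end to the trial. A later cut-off may also be fixed in an analysis plan that is not shown. This stands. What remains is that the only timing in the protocol does not support the estimate and nothing in it commits to a later date. The thin numbers at 24 months are not an error in themselves, since confidence intervals are required and will show the imprecision.

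**One-year OS.** A reader might infer that stale contact also biases this named outcome, by 2 to 3 points under annual contact. That requires living patients to be censored before month 12, which the minimum follow-up in sections 7.10 and 12.1.2 rules out. Once the minimum is enforced, the bias is about zero.

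**One-year PFS.** A reader might infer that it is materially overstated. If progression were found only at scheduled scans, the gap between days 280 and 364 would be worth 4.5 points at a median PFS of 2.6 months, or 1.3 of 30 patients. But sections 7.3 and 7.3.4 provide for scans on clinical suspicion, patients are seen on day 1 of each cycle, deaths count whenever they occur, and the mismatch vanishes when treatment starts on the day of registration. The 4.5 points is a worst case at that median. Larger values need longer assumed medians.

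**Conclusion.** The conflict between sections 3 and 7.10 is direct and needs correcting whatever its numerical effect. With censoring at last contact, it leaves 24-month OS about 5 to 6 points too low under annual contact and about 3 points too low under 6-monthly contact. These figures assume exponential OS with a median of 7.2 to 8.4 months, 18 months of accrual, a cut-off at 30 months, prompt reporting of deaths and no status update at cut-off. If deaths too are learned only at contacts, the bias is smaller.

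The 36-month estimate has 0 of 36 patients behind it at the earliest planned analysis, and no later date is fixed. It is unsupported as planned, not impossible.

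The 1-year scan is a minor mismatch of time origins of 0 to 7 days. The primary outcome, the sample size and the go/no-go rule are not affected.

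**What to change.** 1. Put one survival contact interval after progression in both sections 3 and 7.10. The 6-monthly interval of section 7.10 is preferable because it halves the effect or nearly so.
2. Require the survival status of every living patient to be updated at the data cut-off. This removes the 24-month bias under either interval and makes the 12-month minimum verifiable.
3. In section 12.2, either drop the 36-month estimate at this analysis and give 24 months with the number at risk, or fix a later cut-off that supports 36 months. Eighteen months after the last registration is the bare minimum for one patient to reach it.
4. Minor: use one time origin for PFS and the 1-year CT, or assign the scheduled 1-year scan to the 1-year assessment. Do not read 1-year PFS at month 13. That would add the deaths and symptomatic progressions of an extra month, worth about 1 point (median PFS 2.6 months) to 3 points (median 6 to 12 months) in the opposite direction.

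The cost is wording in sections 3 and 12.2, a short rule for the 1-year scan, and one status request per site at cut-off. A later cut-off, if chosen, costs time.

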There is mounting evidence that iPET is a good predictor of early response in high grade, aggressive B cell NHL. Studies have shown iPET to be an accurate and independent predictor of PFS and OS (29–33). There is an increasing amount of published data using semi-quantitative assessment based on the reduction in the maximum standardised uptake value (Δ SUV max) which may predict outcome more effectively when iPET is performed (34–40). Several multicentre trials are currently exploring the use of Δ SUV to dose intensify treatment in iPET positive patients with DLBCL (35,41).

Glucose metabolism, mTOR pathway inhibition and PET response

PET has the ability to evaluate the metabolic changes that occur in a tumour during treatment. Metabolic changes occur faster and predict response more effectively than assessments of tumour size using CT or MR imaging. Early reduction in FDG uptake has been used to evaluate patient sensitivity to a given treatment regimen when treating a FDG-avid tumour (Warburg effect). The PIK3/AKT/mTOR pathway is considered a 'critical switch', constituting the core of a highly conserved evolutionarily pathway that adjusts protein synthesis to regulate cell growth and proliferation by integrating signals arising from growth factors, hormones, nutrients and energy metabolism (7). One important physiological function of PI3K/AKT/mTOR pathway is to acutely stimulate glucose uptake in response to insulin via glucose transporter 1 (GLUT1) and phosphorylation to glucose-6-phosphate by hexokinase (42). FDG is also transported via GLUT 1 and phosphorylated by hexokinase but then remains trapped in the cell as FDG-6-phosphate is not dephosphorylated unlike glucose-6-phosphate,

giving a signal that can be imaged. Thus FDG imaging with PET-CT may be able to demonstrate PI3K/AKT/mTOR pathway inhibition by agents targeting this pathway.

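### The SUVmax-reduction formula in sections 7.3.5 and 12.2 is bracketed wrongly and, read literally, does not give a percentage reduction (minor; exploratory PET analysis only)

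*Protocol*

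**What the plan says.** Section 12.2 of the protocol (Analysis of Outcome Measures) gives the calculation as "SUVmax reduction (%) = 100 x [SUVmax (PET0) - SUVmax (iPET)/SUVmax (PET screening", after which the round and then the square bracket close. Section 7.3.5 (PET CT scan) prints the same line with the same bracketing. Both sections introduce it as the way the reduction is calculated.

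The quantity has two uses in those paragraphs:

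- A published cut-off is applied to it: "66% at 2 cycles to separate good from poor responders", where a reduction of at least 66% marks a good responder.
- ROC curves are to be derived, to see whether the best cut-off under AZD2014 resembles the one for (R)CHOP.

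Section 1.1 shows what the measure is meant to be: "semi-quantitative assessment based on the reduction in the maximum standardised uptake value".

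Two further statements set the limits of the point. Section 12.2 says: "The biomarker study and PET scan analysis at present are exploratory". Sections 7.3.5 and 12.2 also have all scans read centrally on the visual 5-point scale, and present the semi-quantitative analysis as an addition to that reading.

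**The concern.** The square bracket encloses the difference and the division together. Division binds before subtraction, so the printed expression subtracts a unitless ratio from an SUV and multiplies by 100. A percentage reduction needs the difference grouped first and then divided by baseline.

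The formula also calls the denominator scan PET screening and the first term PET0, and defines neither label. Only one pre-treatment PET is scheduled (sections 5.1.1, 7.3 and 7.3.5), so both must mean that scan.

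Taken literally, the 66% split would hardly separate patients, and the ROC analysis would order them mainly by baseline uptake instead of change. A cut-off found that way could not be compared with 66%. Conversely, an analyst who silently repairs the formula departs from the protocol as written.

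**Working it through.** **Inputs.** The formula (sections 7.3.5 and 12.2, identical) and the cut-off of 66% (same sections). The protocol gives no SUVmax values and no worked example, so there is no figure of its own to reproduce. All SUVmax values below are assumptions for illustration. Write S0 for baseline (screening) SUVmax and Si for interim SUVmax.

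**Two formulas.**

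- As printed: P = 100 x (S0 - Si/S0)
- Relative reduction: R = 100 x (S0 - Si)/S0 = 100 x (1 - Si/S0)

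Subtracting, P - R = 100 x (S0 - 1). The printed value is therefore off by an amount that depends on baseline alone, and the two agree only when S0 = 1.

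**Single patients (assumed values).**

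| S0 | Si | Printed P | Relative reduction R |
|---|---|---|---|
| 20 | 18 | 100 x (20 - 0.9) = 1910% | 100 x 2/20 = 10% |
| 15 | 20 | 100 x (15 - 1.333) = 1367% | 100 x (-5)/15 = -33% |
| 10 | 10 | 100 x (10 - 1) = 900% | 0% |
| 20 | 15 | 100 x (20 - 0.75) = 1925% | 25% |
| 10 | 2 | 100 x (10 - 0.2) = 980% | 80% |

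The last two rows show the ROC problem. The patient with a 25% fall scores 1925 and the patient with an 80% fall scores 980, so their order is reversed.

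**Who meets the 66% cut-off.**

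- As printed: 100 x (S0 - Si/S0) >= 66, so Si/S0 <= S0 - 0.66. A patient with no change (ratio 1) passes once S0 is at least 1.66.
- Relative reduction: Si/S0 <= 0.34, whatever the baseline.

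| Assumed S0 | Largest Si/S0 that passes as printed | Largest Si as printed | Largest Si, relative reduction |
|---|---|---|---|
| 1.5 | 0.84 | 1.26 | 0.51 |
| 2 | 1.34 | 2.68 | 0.68 |
| 3 | 2.34 | 7.02 | 1.02 |
| 5 | 4.34 | 21.7 | 1.7 |
| 10 | 9.34 | 93.4 | 3.4 |
| 20 | 19.34 | 386.8 | 6.8 |

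From a baseline of 3 upward, a patient fails the printed criterion only if uptake more than doubles. At 2 a rise of more than 34% is enough to fail, and at 1.5 an unchanged patient fails.

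**Share of patients passing, under assumed distributions.** Baseline was taken as lognormal (median 5, 10 or 20; log-SD 0.5) and the interim/baseline ratio as lognormal (median 1.2, 0.8 or 0.5; log-SD 0.6).

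| Median baseline | Pass as printed | Pass with relative reduction |
|---|---|---|
| 5 | 93% to 99% | 2% to 26% |
| 10 | 99.4% to 99.98% | 2% to 26% |
| 20 | over 99.9% | 2% to 26% |

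Each range runs over the three assumed median ratios.

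**The case against.** The strongest reply is that the intended meaning is plain. The left side is labelled as a percentage reduction, the cut-off is a published one for that measure, and section 1.1 describes it as a reduction. A reduction cannot exceed 100%, so a value such as 1910% would expose the slip on the first patient. The SUVmax readings come from the scans, so no data are lost and the percentage can be recalculated at any time. This stands, and it is why the point is minor. It does not make the formula right: the line is the protocol's stated calculation, it appears twice, and a correct analysis should not have to depart from it.

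Three stronger readings are tempting but not supported.

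- *That the PET objectives as a whole fail.* Visual 5-point reading is done separately on all scans, and the PET-CT response categories in Appendix 1 do not use this formula. Section 1.1 names both the Deauville criteria and semi-quantitative evaluation as measures of early PET response. Only the latter is touched.
- *That the core lab calculates it this way.* Section 7.3.5 refers to a separate PET-CT manual for further details. That manual is not part of the protocol text, so actual practice is unknown.
- *That nearly every patient would be a good responder, without qualification.* This depends on baseline SUVmax values that the protocol does not give, and it weakens at baselines near 1.5 to 2.

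The two scan labels are a matter of tidiness, since only one scan can be meant.

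**Conclusion.** The formula is wrong as written in both sections. Read literally it overstates the reduction by 100 x (S0 - 1) percentage points for any baseline above 1. It then classes almost every patient with an assumed baseline of about 3 or more as a good responder unless uptake more than doubles. That arithmetic is certain. How many trial patients it would misclassify rests on assumed SUVmax values and on someone applying the line literally, which the protocol does not show.

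The effect is confined to the exploratory semi-quantitative PET analysis: the 66% split at 2 cycles and the ROC comparison with the (R)CHOP cut-off. A reader might infer a threat to the trial's main conclusions. There is none: the primary outcome is CT-based (section 12.1.1), and the formula plays no part in the sample size, the interim rule or the tolerability rules (sections 12.4 and 12.6). Severity is minor.

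**What to change.** In sections 7.3.5 and 12.2 replace the line with:

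SUVmax reduction (%) = 100 x [SUVmax(screening PET) - SUVmax(iPET)] / SUVmax(screening PET)

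Use one name for the baseline scan throughout, and state that iPET is the scan after cycle 2. Check that the PET-CT manual gives the same formula.

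With this wording the 66% cut-off means an interim SUVmax of at most 0.34 times baseline, for example 3.4 or less from a baseline of 10. The cost is one line in each of two sections. No design figure changes and no scan needs to be repeated.
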